5.2 Variables Used for Stratification of Randomization

Approximately 600 subjects will be enrolled to receive ABT-450/r/ABT-267 and ABT-333 with or without RBV depending on their HCV genotype and cirrhotic status. No stratification of randomization is utilized for this study.

6.0 Analysis Conventions

6.1 Baseline and Final Value

6.1.1 Baseline

The baseline value refers to the last non-missing measurement collected before the first dose of study drug. All assessments on Study Day 1 should be performed prior to

administering the first dose of study drug, in accordance with the protocol. The baseline value is therefore determined by the last non-missing measurement collected on or before the first day of study drug administration.

If multiple measurements are recorded on the same day, the last measurement recorded prior to dosing will be used as the baseline value. If these multiple measurements occur at the same time or time is not available, then the average of these measurements (for continuous data) or the worst among these measurements (for categorical data) will be considered as the baseline value. This same baseline value will be used for Treatment and PT Periods.

Safety assessments that are related to a serious adverse event that occurs on the first dose day are excluded when applying this algorithm.

6.1.2 Study Days

Study days (days relative to the first dose of study drug) are calculated for each time point relative to the first dose of study drug. Study Days are negative values when the time point of interest is prior to the first study drug dose day. Study Days are positive values when the time point of interest is after the first study drug dose day. There is no Study Day 0. Study Day 1 is the day of the first dose of study drug.

6.1.3 Study Drug End Days

For all subjects who receive at least one dose of study drug, study drug end days (days relative to the last dose of study drug) are calculated relative to the last dose of study drug. The last day of study drug is defined as Study Drug End Day 0. Days before it have negative study drug end days and days after it have positive study drug end days.

6.1.4 Final Treatment Value

The final treatment value for each subject is the last non-missing measurement collected after Study Day 1 and on or before Study Drug End Day 2.

6.1.5 Final Post-Treatment Value

The final post-treatment value for each subject is the last non-missing measurement collected after Study Drug End Day 2.

6.2 Analysis Windows

For efficacy analyses of HCV RNA and resistance, the time windows specified in [Table 2](#) and [Table 3](#) describe how efficacy data are assigned to protocol-specified time points during the Treatment and PT Periods, respectively. All time points and corresponding time windows are defined based on the blood sample collection date.

For analyses of health-related quality of life (QoL) PROs collected throughout the study, the time windows specified in [Table 4](#) will be used.

For laboratory and vital signs data, the time windows specified in [Table 5](#) and [Table 6](#) describe how data are assigned to protocol specified time points during the Treatment and PT Periods, respectively.

If more than one assessment is included in a time window, the assessment closest to the nominal time will be used. If there are two observations equally distant to the nominal time, the latest one will be used in analyses. The only exception to this is for the SVR windows (e.g., SVR₄, SVR₁₂, and SVR₂₄); for these windows, the last value in the window will be used.

If multiple measurements are made on the same day for a safety laboratory parameter or a vital sign parameter, the average of the values will be used in analyses. For summaries of shifts from baseline and potentially significant values, multiple values on the same day will not be averaged; all values will be considered for these analyses.

Table 2. Analysis Time Windows for HCV RNA and Resistance Endpoints (Treatment Period)

Scheduled Visit	Nominal Day (Study Day)	Time Window (Study Day Range)
Day 1/Baseline ^a	1 ^a	≤ 1 ^a
Week 2	14	2 to 21
Week 4	28	22 to 56
Week 12	84	57 to 126
Week 24 ^b	168	127 to 182
Final Treatment Visit ^c		2 to ≤ 2 days after last dose of study drug

a. Day of first dose of study drug.

b. Week 24 Visit is only applicable to subjects assigned to 24 weeks of treatment.

c. The last value within the window will be used to define the Final Treatment visit value. The upper bound of this Final window is Study Drug End Day ≤ 2.

Note: Data must also have Study Drug End Day ≤ 2 for all windows. The result closest to the scheduled time point will be used.

Table 3. Analysis Time Windows for HCV RNA and Resistance Endpoints (Post-Treatment Period)

Scheduled Visit^a	Nominal Day (Study Drug End Day)	Time Window (Study Drug End Day Range)
Post-Treatment Week 4	28	3 to 56
Post-Treatment Week 12	84	57 to 126
Post-Treatment Week 24	168	127 to 266
Post-Treatment Week 52	364	267 to 546
Post-Treatment Week 104	728	547 to 910
Post-Treatment Week 156	1092	911 to 1274
Post-Treatment Week 208	1456	1275 to 1638
Post-Treatment Week 260	1820	1639 to 2002
SVR ₄ ^b	28	3 to 56
SVR ₁₂ ^b	84	57 to 126
SVR ₂₄ ^b	168	127 to 210

a. Post-Treatment Visits are applicable for subjects who received at least one dose of study drug.

b. For SVR windows, the last value in the window will be used.

Note: The result closest to the scheduled time point will be used, except for SVR₄, SVR₁₂, and SVR₂₄. Data must also have Study Drug End Day > 2 for all windows. Study Drug End Day 0 is defined as the day of the last dose of study drug.

Table 4. Analysis Time Windows for PRO Instruments

Scheduled Visit ^a	Nominal Day (Study Day)	Time Window (Study Days Range)
Day 1/Baseline	1 ^b	≤ 1 ^b
Week 4	28	2 to 56
Week 12	84	57 to 126
Week 24 ^c	168	127 to 182
Final Treatment Visit ^d		2 to ≤ 2 days after last dose of study drug

Scheduled Visit	Nominal Day (Study Drug End Day)	Time Window (Study Drug End Days Range)
Post-Treatment Week 4	28	3 to 56
Post-Treatment Week 12	84	57 to 126
Post-Treatment Week 24	168	127 to 266
Post-Treatment Week 52	364	267 to 546
Post-Treatment Week 104	728	547 to 910
Post-Treatment Week 156	1092	911 to 1274
Post-Treatment Week 208	1456	1275 to 1638
Post-Treatment Week 260	1820	1639 to 2002
Final Post-Treatment Visit ^e		> 2 days after last dose of study drug

a. SF-36v2 and FACIT-F are collected at Baseline, Week 4, Week 12 and Week 24 (only for subjects with 24 weeks of treatment), and Post-Treatment Weeks 4, 12, 24, 52, 104, 156, 208 and 260.

b. Day of first dose of study drug.

c. Applicable to subjects with 24 weeks of treatment.

d. The last value within the window will be used to define the Final Treatment visit value. The upper bound of this Final window is Study Drug End Day ≤ 2.

e. The last value within the Post-Treatment Period window will be used to define the Final Post-Treatment visit value. The lower bound of this Final window is Study Drug End Day 3.

Note: The result closest to the scheduled time point will be used. For visits through Treatment Week 24, data must also be within 2 days of the last dose of study drug. For post-treatment visits, data must also have Study Drug End Day > 2 where Study Drug End Day 0 is defined as the day of the last dose of study drug.

Table 5. Laboratory Data and Vital Sign Visit Windows (Treatment Period)

Scheduled Time	Nominal Day (Study Day)	Time Window (Study Days Range)
Day 1/Baseline ^a	1	≤ 1
Week 2	14	2 to 21
Week 4	28	22 to 56
Week 12	84	57 to 126
Week 24 ^b	168	127 to 182
Final Treatment Visit ^c		2 to ≤ 2 days after last dose of study drug

a. Day of first dose of study drug.

b. Applicable to subjects with 24 weeks of treatment.

c. The last value within the window will be used to define the final on-treatment value. The upper bound of this Final window is Study Drug End Day ≤ 2.

Note: The result closest to the scheduled time point will be used. Data must also be ≤ 2 days of the last dose of study drug. Total Insulin is measured at baseline, Week 12, Week 24 (for subjects on 24-week treatment regimen only), or EOT, and will use those visit windows as defined above.

Table 6. Laboratory Data and Vital Sign Visit Windows (Post-Treatment Period)

Scheduled Time	Nominal Day (Study Drug End Day)	Time Window (Study Drug End Days Range)
Post-Treatment Week 4	28	3 to 56
Post-Treatment Week 12	84	57 to 126
Post-Treatment Week 24	168	127 to 266
Post-Treatment Week 52	364	267 to 546
Post-Treatment Week 104	728	547 to 910
Post-Treatment Week 156	1092	911 to 1274
Post-Treatment Week 208	1456	1275 to 1638
Post-Treatment Week 260	1820	1639 to 2002
Final Post-Treatment Visit ^a		> 2 days after last dose of study drug

a. The last value within the Post-Treatment Period window will be used to define the final post-treatment value. The lower bound of this Final window is Study Drug End Day 3.

Note: The result closest to the scheduled time point will be used. Data must also have Study Drug End Day > 2. Vital signs and hematology, chemistry, urinalysis, and coagulation panels are collected at every Post-Treatment Period visit. Total Insulin is collected at Post Treatment Weeks 52, 104, 156, 208, and 260 and will use those visit windows as defined above. FibroTest samples are collected at Post-Treatment Weeks 12 and 24 (or upon study discontinuation) and will use those visit windows as defined above.

6.3 Missing Data Imputation

No data will be imputed for any efficacy or safety analyses except for the PRO questionnaires, for analyses of the HCV RNA endpoints, and for analysis of the persistence of resistance. If a respondent answers at least 50% of the items in a multi-item scale of the SF-36v2, the missing items will be imputed with the average score of the answered items in the same scale. In cases where the respondent did not answer at least 50% of the items, the score for that domain will be considered missing. Similarly, the missing items of the FACIT-F questionnaire will be imputed with the average score of the answered items in the same scale as long as more than 50% (≥ 7 out of 13) of the items in the scale are answered. The SF-36v2 Mental and Physical Component Summary measures will not be computed if any domain is missing.

HCV RNA values will be selected for an SVR analysis based on visit windows as defined in Section 6.2. When there is no HCV RNA value in a visit window based on defined visit windows, the closest values before and after the window, regardless of the value chosen for the subsequent and preceding window, will be used for the flanking imputation described below.

If a subject has a missing HCV RNA value at a post-Day 1 visit but with undetectable or unquantifiable HCV RNA levels at both the preceding value and succeeding value, the HCV RNA level will be considered undetectable or unquantifiable, respectively, at this visit for this subject. In addition, if a subject has an unquantifiable HCV RNA level at the preceding value and an undetectable HCV RNA level at the succeeding value, or vice versa, the HCV RNA level will be imputed as unquantifiable at this visit for this subject. For SVR analysis, if there is no value in the appropriate window after flanking imputation but there is an HCV RNA value after the window, then it will be imputed into the SVR window. Subsequent to this flanking imputation, if a subject is missing a value for the visit window associated with the analysis, the subject will be imputed as a visit failure (i.e., not undetectable or unquantifiable).

If a subject starts another treatment for HCV, then all HCV RNA values for this subject measured on or after the start date of the new HCV treatment will be excluded from analyses. The subject will be considered a failure for summaries of viral response at all time points after the start of the new HCV treatment.

HCV RNA < LLOQ Analyses for SVR

If a subject is missing an HCV RNA value for the visit window associated with the analysis of SVR after performing the imputations described above, then this value will be imputed with an HCV RNA value from a local laboratory if present; otherwise, the HCV RNA value for this visit will be missing. Subjects with missing HCV RNA data in the analysis window, after imputations, will be imputed as a failure.

HCV RNA Analyses for Relapse and Virologic Failure

If HCV RNA values from the central laboratory are missing but a local laboratory value is present in the appropriate time period, then the local laboratory value will be used to assess post-treatment relapse and on-treatment virologic failure.

Finally, missing sequence data will be imputed as follows in the analysis of the persistence of resistance from the sequences from PT Week 52 through PT Week 260 (5 years). If a signature variant is not detectable by population, clonal or deep sequencing at PT Week 24 (or later), the variant is imputed as not detectable at the PT Week 52 (or timepoints after the sequence with the variant not detectable) and time points thereafter if a sample from Post-Treatment Week 52 or later is not sequenced. If a signature variant is detectable by population, clonal, or deep sequencing at Post-Treatment Week 52 or later, then the variant is imputed as being detectable at earlier time points if the sample at the earlier time point is not sequenced.

7.0 Demographics, Baseline Characteristics, Medical History, and Previous/Concomitant Medications

Demographics, baseline characteristics, medical history, and previous/concomitant medications will be summarized overall and by presence of cirrhosis and genotype 1 subtype on the safety population.

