10.0 Efficacy Analysis

10.1 General Considerations

The primary efficacy analysis on clinical outcomes will be performed on all subjects in the ITT population as defined in Section 5.1. All other efficacy analyses will be performed on the ITT-II population.

Treatment effects will be evaluated based on a two-sided significance level of 0.05 (when rounded to three decimal places). The data from the ITT-II population will be presented in one column/row as it represents the labelled treatment.

Plasma HCV RNA levels will be determined for each sample collected by the central laboratory using the COBAS[®] AmpliPrep/COBAS[®] TaqMan[®] HCV Test, v2.0. The lower limit of quantification (LLOQ) and the lower limit of detection (LLOD) is 15 IU/mL. HCV RNA results that are detectable but not quantifiable are reported as "< 15 IU/mL" and results that are not detectable are reported as "-NON-DETECTED."

Assessment of Clinical Outcomes

Incidence of the following clinical outcome events will be collected during the 12/24 weeks of treatment and the 5-year (PT Week 260) Post-Treatment Period. The data reported on the "Clinical Outcome" eCRFs will be adjudicated by an independent outcome committee and results of the adjudication will be added to the "Clinical Outcome" eCRFs:

- All-cause death: Death due to any cause.
- Liver-related death: Death as the result of a liver-related cause.
- Liver decompensation: Development of any of the following conditions: ascites, hepatic encephalopathy, or variceal bleeding.

- Liver transplantation: any subject who had a liver transplantation
- Hepatocellular carcinoma (HCC): development of HCC in any subject at any time during the study. HCC is defined by histologic confirmation or a > 1 cm mass lesion on cross-sectional imaging that meets the diagnostic criteria for HCC according to EASL guidelines.
- Composite of any of the above outcomes.

Definitions for HCV RNA Efficacy Endpoints

Note that a confirmed quantifiable post-treatment value is defined as two consecutive post-treatment HCV RNA measurements \geq LLOQ. During treatment, a confirmed quantifiable value is defined as any two consecutive HCV RNA values \geq LLOQ, either both during treatment or at the final treatment measurement and the next consecutive post-treatment measurement.

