10.3 Primary Efficacy Analysis

The primary efficacy analysis will be conducted among subjects in the ITT population as described in Section 5.1. HCV RNA values and SVR₁₂ will be imputed as described in Section 6.3.

The primary efficacy endpoint is to assess the effect of response to treatment (as assessed by SVR₁₂ status) on clinical outcomes by comparing the time to incidence of the following events between subjects who achieve SVR₁₂ and those who do not.

- All-cause death
- Liver-related death
- Liver decompensation
- Liver transplantation
- Hepatocellular carcinoma

- Composite of any of the above outcomes

For each of the six event types as listed above, a subject's time to event will be defined as the number of days from the first day of study drug dosing for the subject to the day the subject experiences an event of interest. All events of interest will be included, regardless of whether the event occurred while the subject is still taking study drug or has previously discontinued study drug. If the subject does not experience an event of interest nor has the subject died (all-cause death), the subject's data will be censored at the date of the subject's last available assessment of clinical outcomes. For subjects with no post-baseline assessment, the subject's data will be censored on the first day of study drug dosing. All-cause death is a censoring event for liver-related death, liver decompensation, liver transplantation and hepatocellular carcinoma. Time to the composite of clinical outcomes is the time to the first occurrence of any clinical outcome.

For each of the six event types, the distribution of time to event will be estimated for subjects who have achieved SVR₁₂ and those who haven't using Kaplan-Meier methodology and compared between the subjects who have achieved SVR₁₂ and those who haven't using the log-rank test.

For each of the six event types, the 1-, 2-, 3-, 4-, and 5-year event-free survival rate will be estimated using Kaplan-Meier methodology and a 95% confidence interval will be constructed separately for those who have achieved SVR₁₂ and those who have not. For each of the six event types, a Cox proportional hazards (PH) model will be constructed to include all the baseline characteristics as described in Section 7.1, SVR₁₂ status, and other variables as appropriate.

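### SAP 6.3 ranks a local HCV RNA result measured inside the SVR window below values imputed from outside it, so SVR12 can contradict the in-window measurement (minor).

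*SAP*

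**What the plan says.** SAP 6.2 ties windows to the draw date: "All time points and corresponding time windows are defined based on the blood sample collection date". The SVR12 window is Study Drug End Day 57 to 126, and "For SVR windows, the last value in the window will be used". SAP 10.1 names the routine source: "Plasma HCV RNA levels will be determined for each sample collected by the central laboratory".

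For an empty window, SAP 6.3 starts with flanking, which uses "the closest values before and after the window, regardless of the value chosen for the subsequent and preceding window" and succeeds when both are below LLOQ. Carry-back comes next. It applies "if there is no value in the appropriate window after flanking imputation but there is an HCV RNA value after the window", with no latest day given. A separate paragraph for SVR then brings in the local laboratory: "after performing the imputations described above, then this value will be imputed with an HCV RNA value from a local laboratory if present". If the window is still empty, the subject is a failure.

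The following paragraph, on relapse and virologic failure, has a different rule for absent central values, and no imputation comes first: "a local laboratory value is present in the appropriate time period, then the local laboratory value will be used to assess post-treatment relapse".

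SAP 10.3 carries the result into the primary analysis: "HCV RNA values and SVR₁₂ will be imputed as described in Section 6.3". Protocol 8.1 has flanking and carry-back but no local-laboratory step, so the SAP is the only source for this rule.

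**The concern.** SAP 10.1 defines SVR12 by HCV RNA in the SVR12 window. Where a local laboratory has measured HCV RNA in that window, the endpoint is observed and nothing needs to be imputed. SAP 6.3 nevertheless lets values from outside the window decide first, and they can contradict the measurement in either direction.

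Three things are at stake:

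- SVR12 is the first-listed secondary endpoint, and it forms the two groups of the primary comparison, where only about 4% of subjects are expected in the non-SVR12 group.
- The relapse rule reads the local value directly, so one subject's SVR12 status, relapse status and reason for non-response may rest on different samples.
- Carry-back and flanking both need a later value. One that arrives after the interim lock can reverse the SVR12 status reported at the interim analysis.

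**Working it through.** **Inputs.** SVR12 window Day 57 to 126 (SAP Table 3). Order of steps from SAP 6.3: in-window central value, flanking, carry-back, local value, failure. Two assumptions are needed. Flanking and carry-back use central values only; this is inferred from SAP 10.1 and from the fact that a separate local step would otherwise be redundant. Carry-back takes the nearest later value.

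**Applying the rule.** None of these subjects has a central value in Day 57 to 126.

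| Subject | Central values | Local value | SAP 6.3 | In-window local value used first |
|---|---|---|---|---|
| A | Day 28 < LLOQ; Day 168 ≥ LLOQ | Day 84 < LLOQ | Flanking fails; Day 168 carried back: failure | SVR12 |
| B | Days 28 and 168 < LLOQ | Day 84 ≥ LLOQ | Flanking succeeds: SVR12 | Not SVR12 |
| D | Day 28 < LLOQ; nothing later | Day 84 < LLOQ | Local value used: SVR12 | SVR12 |

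A and B are misclassified relative to the measured value. D shows that the local step works when no later central value exists.

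**Consistency with other definitions.** Suppose A completes treatment and the Day 168 viraemia is confirmed.

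- A is not a Relapse12, because no quantifiable value falls at or before the SVR12 time point.
- A is not a Relapse24, because that category is limited to subjects who achieved SVR12.
- Among the SVR24 reasons A falls into the residual category.
- Among the SVR12 reasons A is either missing follow-up or residual, depending on whether the local sample counts as data. If missing, and if SAP 10.6 means the same category, A also leaves the mITT-GT + VF sensitivity analysis.

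B matches the pattern that SAP 10.1 itself gives as an example of non-response: a single quantifiable value in the window, then an undetectable one (taking B's Day 168 value as undetectable). B's class therefore depends on which laboratory ran the sample.

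**Interim against final.** If the Day 168 value is not yet in the interim database, neither flanking nor carry-back is possible and the local value is used: A is SVR12 and B is not. Once Day 168 is added, both reverse.

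**Size.** The documents do not say how often local results occur. For route A, assume that 1–3% of subjects have only a local result in the window and that 1–5% of those are viraemic at the next central sample:

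- This study: 600 × 0.01 × 0.01 = 0.06 to 600 × 0.03 × 0.05 = 0.9 subjects.
- Pooled (1,650 + 600 = 2,250): 2,250 × 0.01 × 0.01 = 0.2 to 2,250 × 0.03 × 0.05 = 3.4 subjects.

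Route B has no estimate.

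Each reclassified subject moves SVR12 by 1/600 = 0.17 percentage points. At the planning rate of 96%, 576/600 = 96.00% (Wilson 95% CI 94.12 to 97.30) becomes 575/600 = 95.83% (93.92 to 97.16).

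**The case against.** The best defence is that putting the central laboratory first is deliberate. Protocol and SAP specify one central assay with an LLOQ of 15 IU/mL. A local LLOQ is unspecified, so a local result below its own limit may not meet the endpoint. The protocol has no local step, and the SAP adds one only as a last resort. The assay point stands as a reason to flag these subjects. It does not justify the order, because the SAP already accepts local values for SVR, relapse and virologic failure.

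It is also fair to say that A's relapse is not lost: Relapse_overall does not require SVR12, and SAP 10.7 lists completers who relapse in the SVR24 window or at any time post-treatment. The damage is limited to SVR12 status and the time-specific labels. Route A also requires the later viraemic value to precede any new HCV treatment, since SAP 6.3 excludes values from then on.

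A reader might infer three stronger points, which the documents do not support:

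- **That the local result is never used**, because the general text of 6.3 imputes failure before the local step is reached. With 10–30% of local-only subjects lacking a later central value, that would cost 0.01 × 0.10 to 0.03 × 0.30, or 0.1 to 0.9 points of SVR12. But the specific SVR paragraph places failure after the local step, and Subject D is SVR12.
- **That an early local value can count as SVR12**, because the SVR sentence states no day range. The sentence fills a value missing for the analysis window, windows follow the draw date, and SVR12 is defined within its window. This is a missing clarifying phrase.
- **That the primary hazard ratio drifts towards 1**, from 0.25 to at most 0.25 × (90 + 3.4)/(90 + 0.25 × 3.4) = 0.257, with 90 = 4% of 2,250. That gives subjects who are later viraemic the responder hazard for the whole follow-up. Nothing in the documents supports this; if they carry the non-responder hazard, moving them causes no dilution.

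**Conclusion.** The point holds as a minor defect in the order of steps. As written, SAP 6.3 lets values from outside the window override a local HCV RNA result measured inside it, in both directions. The adjacent relapse rule does not do this, so classifications can disagree and SVR12 status can change between the interim and final analyses.

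The conclusion rests on the inference that flanking and carry-back use central values only. The size rests on assumed frequencies: for route A, probably fewer than one subject in this study, at 0.17 points of SVR12 per subject. No loss of 0.1 to 0.9 points in SVR12 and no hazard-ratio bias is claimed. The reason to act is that an observed endpoint should not be replaced by an imputed one when the remedy is a change of wording.

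**What to change.** Restate SAP 6.3 as one ordered list for SVR4, SVR12 and SVR24:

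1. Central value in the window.
2. If missing, local value collected in the same window (Study Drug End Day 57 to 126 for SVR12).
3. Flanking.
4. Carry-back of the next later value.
5. Failure.

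Delete the local step that now follows imputation, and the earlier mention of failure. State that the same in-window value serves SVR, relapse and the reason for non-response. List the subjects classified from a local value, with the local LLOQ where known, because it may differ from 15 IU/mL.

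The cost is SAP wording, a few lines of programming and one listing. No new data are needed. Because SVR12 groups the pooled primary analysis, the same order should apply to the TOPAZ-I subjects in it.
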